#### 5. Analysis Populations

The following analysis populations are planned for this investigation:

- Screening: All subjects who provide informed consent and demographic and/or Baseline screening assessment results, regardless of the subject's randomization and treatment status in the investigation.
- Safety (SAFT): All subjects who receive at least 1 treatment with RHA® 3 or
- Modified intent-to-treat (mITT) analysis set will be used for effectiveness analysis. The mITT set is based on the conventional intent-to-treat (ITT) analysis set:

- 6. General Issues for Statistical Analysis
- 6.1. Statistical Definitions and Algorithms

#### 6.1.1. Baseline

For all effectiveness and safety endpoints (for which a Baseline data is applicable), the last nonmissing observation recorded prior to first study treatment administration will be used as the Baseline observation for all calculations. If no observation is available prior to first study treatment administration, then Baseline value is considered missing and protocol deviation is recorded.

State of the second	
U	

#### 6.1.4. Analysis Visit Windows

Statistical analyses will be based on scheduled visit as collected in the electronical Case Report Form (eCRF) without further realignment.

#### 6.1.6. Derived Variables

The following derived and computed variables have been initially identified as important for the analysis of effectiveness.

It is expected that additional variables will be required. The SAP will not be amended for additional variables that are not related to the primary or secondary target variables. Any additional derived or computed variables will be identified and documented in the SAS programs that create the analysis files. If the SAP is not amended, further derivations related to primary and secondary target variables will be described in the CSR.

#### 6.1.6.1. Responder Rate

Definition of responder: ≥1-grade point on the TLFS 12 weeks after the last treatment when compared to pretreatment (Baseline). A positive change from Baseline value is considered as improvement.

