	Subjects who had entered the study under earlier versions of the CIP (version and earlier) and who do not agree with the extension of their participation in th study as per CIP version 5.0, to 52 weeks after last injection, will be allowed to continue with the visits as originally planned. They will exit the study at the study at weeks after last injection) or, if they receive retreatment they will have follow-up telephone call and will exit the study 4 weeks after retreatment. Further details are described in the CIP.
	A BLE will conduct assessments of effectiveness during the study, including assessment of the primary endpoint 12 weeks after the last treatment The BLE will conduct effectiveness evaluations at 15 36 weeks after the last treatment), 152 weeks after the last treatment), and 154 weeks after the retreatment, if applicable).
PRIMARY EFFECTIVENESS ENDPOINT	The effectiveness of RHA [®] 3 will be demonstrated if the change from Baseline for subjects treated with RHA [®] 3 is statistically non-inferior to the change from Baseline for subjects treated with EXECUTE at 12 weeks after the last treatment as assessed by the BLE using the TLFS. The difference in the TLFS change from Baseline to 12 weeks will be used to establish non-inferiority.
	A change in the TLFS ≥ 1 grade compared to pretreatment will be considered clinically meaningful.
SECONDARY EFFECTIVENESS ENDPOINTS	 TLFS change from Baseline assessed: By the BLE at Visit 4 and each visit at the study site afterwards
	 Responder rate calculated using TLFS assessed: By the BLE at Visit 4 and each visit at the study site afterwards

Tinical Investigation Plan	Confidential
INVESTIGATIONAL PRODUCT NAME	RHA® 3
CLINICAL INVESTIGATION PLAN (CIP) NUMBER	
	 A responder will be defined as a subject who has a ≥1 grade improvement or the TLFS. Subject satisfaction using the Subject Satisfaction Scale at each visit at the study site starting at Visit 2
	 FACE-Q scores for each module (satisfaction with lips and satisfaction with outcome) assessed by the subject at each visit at the study site
	GAIS as assessed:
	• By the BLE starting at Visit 4 and each visit at the study site afterwards
SAFETY ENDPOINT	Adverse Events
	Post-injection CTR from the subject's day diary

Page 8 of 132

Confidential

Clinical Investigation Plan

I

INVESTIGATIONAL PRODUCT NAME	RHA [®] 3
CLINICAL INVESTIGATION PLAN (CIP) NUMBER	

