6.2.4. Safety Objective

• To assess the safety of RHA[®] 3 in subjects after lip augmentation

Confidential

	Objectives	Endpoints
Pr	imary effectiveness	
•	To assess the effectiveness (non- inferiority) of RHA [®] 3 versus control of the set of	 The effectiveness of RHA[®] 3 will be demonstrated if the change from Baseline for subjects treated with RHA[®] 3 is statistically non-inferior to the change from Baseline for subjects treated with at 12 weeks after the last treatment as assessed by the BLE using the TLFS. The difference in the TLFS change from Baseline to 12 weeks will be used to establish non-inferiority
Se	condary effectiveness	
•	To assess the effectiveness of RHA® 3 versus and fullness to the lips in subjects seeking lip augmentation up to 52 weeks	 TLFS change from Baseline assessed: By the BLE at Visit 4 and each visit at the study site afterwards
•	To assess the responder rate of RHA® 3 versus augmentation up to 52 weeks	 Responder rate calculated using TLFS assessed: By the BLE at Visit 4 and each visit at the study site afterwards A responder will be defined as a subject who has a ≥1-grade improvement on the TLFS
•	To assess the subject satisfaction and patient-reported outcome of the aesthetic procedure (FACE-Q) with RHA [®] 3 versus Constant of after lip augmentation up to 52 weeks	 Subject satisfaction using the Subject Satisfaction Scale at each visit at the study site starting at Visit 2 FACE-Q scores for each module (satisfaction with lips and satisfaction with outcome) assessed by the subject at each visit at the study site
•	To assess the GAIS of RHA [®] 3 versus Control of Control of Cont	 GAIS as assessed: By the BLE starting at Visit 4 and each visit at the study site afterwards

Table 6-1Objectives Mapped to Endpoints

Page 40 of 132

Page 41 of 132

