#### 2.2.1.2. Secondary Effectiveness Endpoints

The secondary effectiveness endpoints are:

- TLFS change from Baseline assessed:

   By the BLE at each visit at the study from Visit 4
- Responder rate calculated using TLFS assessed:
   O By the BLE at each visit at the study from Visit 4

A responder will be defined as a subject who has a  $\geq 1$  grade improvement on the TLFS.

• Subject satisfaction using the Subject Satisfaction Scale at each visit at the study site starting at Visit 2

FACE-Q scores for each module (satisfaction with lips and satisfaction with outcome) assessed by the subject at each visit

- GAIS as assessed:
  - o By the BLE starting at each visit at the study from Visit 4

Statistical Analysis Plan Protocol Number	

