#### 8.3.2. Responder Rate Based on TLFS

Responder rate will be tabulated by treatment group: frequency of responders, percentage of responders along with 95% CI will be tabulated. Fisher's exact test will be performed to compare responder rates at each applicable visit.

The following categories are used:

- Responder
- Non-responder.

Page 34 of 53

GAIS grade frequencies and percentages will be calculated and presented for each study visit.

The GAIS is a subjective 5-grade dynamic scale as detailed below, will be assessed by Investigators and subjects.

Grade description:

- 1. Much improved
- 2. Improved
- 3. No change
- 4. Worse
- 5. Much worse

,		
	the second s	

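### SAP 6.1.6.1 fixes responder status at Week 12, which contradicts the by-visit responder endpoint and its 52-week objective

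*SAP*

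**What the plan says.** SAP 6.1.6.1, under the derived variables, gives the rule for the responder flag: "Definition of responder: ≥1-grade point on the TLFS 12 weeks after the last treatment when compared to pretreatment (Baseline". It adds the direction of scoring, "A positive change from Baseline value is considered as improvement", and names no rater.

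The endpoint itself is stated differently elsewhere:

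- SAP 2.2.1.2 lists the endpoint as "Responder rate calculated using TLFS assessed", with the schedule "By the BLE at each visit at the study from Visit 4". It then says "A responder will be defined as a subject who has a" gain of at least 1 grade, with no time attached.
- Protocol 2.1 sets the schedule as "By the BLE at Visit 4 and each visit at the study site afterwards". Protocol Table 6-1 says "A responder will be defined as a subject who has a ≥1-grade improvement on the TLFS", again with no time point.
- Protocol 6.2.2 and Table 6-1 carry the responder objective to 52 weeks.
- SAP 8.3.2 plans the comparison: a Fisher's "exact test will be performed to compare responder rates at each applicable visit".

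**The concern.** Section 6.1.6 is where a programmer looks to build the responder flag. A flag fixed at Week 12 gives each subject one status for the whole study. An endpoint assessed at every visit needs one status per visit. The later visits are the ones that answer the 52-week objective, because they show whether response lasts.

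Timing adds to this. SAP 6.1.6 says that if the SAP is not amended, further derivations for primary and secondary variables will be described in the study report. The choice between the two definitions could then be documented only after the data are unblinded, which sits badly with a plan that SAP Section 1 describes as set in advance.

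**Working it through.** This is a check of definitions. The plan gives no figure to reproduce.

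**Visits.** Protocol Section 7 places Visit 4 at 12 weeks after the last treatment. SAP 3.1 has the BLE assess again at 36 weeks, at 52 weeks and, where applicable, 4 weeks after retreatment. Parts of the schedule are blacked out, so there may be others.

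**Inputs for a change score.** SAP 6.1.1 fixes one Baseline for all calculations, the last non-missing value before first treatment. SAP 6.1.4 analyses by scheduled visit as collected. For visit v, let D(v) = BLE TLFS grade at v minus BLE Baseline grade.

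**The two rules.**

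- Rule A (SAP 6.1.6.1): responder if D(Week 12) ≥ 1.
- Rule B (SAP 2.2.1.2, Protocol Table 6-1): responder at v if D(v) ≥ 1.

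At v = Week 12 the rules are the same. At later visits they compare as follows:

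| Subject | D(Week 12) | D(Week 52) | Rule A, Week 12 status repeated | Rule B at Week 52 |
|---|---|---|---|---|
| Response kept | 1 | 1 | responder | responder |
| Response lost | 1 | 0 | responder | non-responder |
| Response gained late | 0 | 1 | non-responder | responder |
| No response | 0 | 0 | non-responder | non-responder |

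The change scores are illustrative. The middle two rows show that the rules can disagree in either direction.

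**Group level.** Among subjects assessed at both visits, let L be the proportion who lose response between Week 12 and v, and G the proportion who first gain it. If the Week 12 status were repeated at v, then

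reported rate − rate under Rule B = L − G,

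which is the net loss of response after Week 12. It is zero only when L = G. The documents give neither L nor G, so no number follows. The other literal reading of Rule A is that status does not exist after Week 12. Under that reading Week 12 is the only visit to which 8.3.2 applies, and the later rates are not produced.

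**Which text governs.** The visible SAP states no order of precedence between 6.1.6.1 and 2.2.1.2. Section 1 names the protocol as the reference document, which favours Rule B without settling the point.

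**The case against.** The strongest reply is that a sensible analyst would use Rule B. The documents supply a time-free definition, later BLE ratings, a single Baseline, analysis by scheduled visit and a comparison worded for several visits. Nothing says that the Week 12 status is carried forward, and repeating one fixed flag would make the by-visit tests pointless. This stands. A reader might infer from 6.1.6.1 that the later responder rates cannot be computed, or that the 52-week objective will go unanswered or be overstated. The documents do not support either inference.

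The reply also limits the impact. Protocol 11.4 calls the secondary analyses descriptive. SAP 8.3.1 summarises BLE TLFS grade and change from Baseline at each visit, so a waning effect would show there whatever the flag does. That stands too, although a mean change is not a responder rate and does not replace the stated endpoint.

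Finally, the public copy is blank where the schedule and planned tables would be, so the visits meant in 8.3.2 may be listed in hidden text. The visit wording in 8.3.2 therefore cannot be faulted as unspecified. This does not rescue 6.1.6.1, whose sentence is complete and names one time point.

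**Conclusion.** The contradiction is real and minor. A stated derivation rule conflicts with the endpoint it is meant to serve, with the objective's 52-week horizon and with the planned by-visit tests. The Week 12 responder rate is the same under both definitions. The primary analysis of TLFS change at Week 12 does not use the flag. Only responder rates after Week 12 are exposed, and only if 6.1.6.1 is followed literally. The size of any error would then be the net loss of response after Week 12, which the documents do not allow anyone to estimate.

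The conclusion rests on the visible text. It assumes that no hidden passage redefines response by visit or states which definition takes precedence.

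**What to change.** In SAP 6.1.6.1, replace the Week 12 time point with the visit being analysed. Suggested wording:

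> Responder at a visit: BLE TLFS grade at that visit minus BLE Baseline grade ≥ 1, derived separately at Visit 4 and at each later site visit.

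Naming the BLE matters because Protocol 8.2.2.1 has the treating investigator rate the TLFS as well. The existing sentence on the direction of change can stay.

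In SAP 8.3.2, make the applicable visits refer to this same set. Keep the visit 4 weeks after retreatment, since the endpoint covers every later site visit, but report it separately from the visits up to 52 weeks. SAP 3.1 offers retreatment with RHA 3 whatever the original group, so that visit does not compare the two products as randomised.

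The cost is a few lines of SAP text and the matching derivation. No new data are needed, because the BLE assessments are already planned. Make the change before database lock and unblinding, so that the choice of definition is not left to the study report.

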#### 6.1.6.2. FACE-Q Scores

For FACE-Q (Satisfaction with Lips and Satisfaction with Outcome), the outcome of all the question of each domain, described below, will be pooled and data will be transformed so that higher scores reflected superior (positive) outcome and adapted to a scale of 100 units (i.e., worst/lowest score = 0, best/highest score = 100). Transformation of scores will be done according to FACE-Q manual.

Page 25 of 53

	Statistical Analysis Plan	1
	Protocol Number	
		1
		8
_		

Page 26 of 53

Statistical Analysis Plan	

I

Page 27 of 53

Statistical Analysis Plan Protocol Number	

### 6.1.6.3. Adverse Device Effect

An adverse device effect (ADE) is any AE with a relationship to the study procedure or study device recorded in the eCRF as 'Possibly related' or Probably related' or 'Causal relationship'. An AE with missing or not assessable relationship will be considered as 'treatment related (probably related)'. AEs will be tabulated by all relationship categories recorded in eCRF.

#### 6.1.6.4. CTRs

Page 28 of 53

#### 6.1.6.5. Prior and Concomitant Medications

Medications that started prior to the first study treatment will be considered prior medications. A concomitant medication is defined as any medication that was administered during the treatment period. This includes medications that started before the treatment period and continued while on treatment and medications that started during the treatment period.

If the start/stop dates of a medication are partially or completely missing, then the medication will be assumed to be concomitant if it cannot be definitely shown that it was not administered during the treatment period. Missing dates will not be replaced.

#### 6.1.7. Data Adjustments/Handling/Conventions

All collected data will be presented in listings.

Data not subject to analysis according to this plan will not appear in any tables or graphs but will be included only in the data listings.

All P values will be displayed in 4 decimals and rounded using standard scientific notation (e.g., 0.XXXX). If a P value less than 0.0001 occurs, it will be shown in tables as < 0.0001.

For missing adverse events onset dates and times, the convention for replacing missing dates for the purposes of calculating derived variables is as follows:

For partial AE start dates:

- If the year is unknown, then do not impute the date but assign a missing value.
- If the month and day are unknown, then:
  - o If the year matches the year of injection date, and the end date (if present) is after
  - injection date, then impute as the month and day of the injection date.
  - o Otherwise, assign January.
- If the month only is unknown, then:
  - If the year matches the year of injection date and day is on or after day of injection, then assign the month of injection. If this produces a date after the AE end date, assign the month before.
  - If the year matches the year of injection date and day is before day of injection, then assign the month after injection. If this produces a date after the AE end date, assign the month of injection.
  - o Otherwise, assign January.
- If the day is unknown, then:
  - If the month and year match the month and year of the injection date, then impute as the day of injection date. If this produces a date after the AE end date, assign 01.
  - Otherwise, assign 01.

For partial AE end dates:

- If the year is unknown, then do not impute the date but assign as a missing value. At the time of the analysis, an AE with a complete missing end date will be considered ending at the cut-off date of the analysis in order to derive the duration.
- If the month is unknown, then assign December. If this produces a date after the last contact date, assign this date.
- If the day is unknown, then assign the last day of the month. If this produces a date after the last contact date, assign this date.

If partial times occur, the convention is as follows:

- if the missing time occurs on the day of the first dose and both the hour and minute are missing then the time assigned is the time of the first dose, otherwise if both the hour and minute are missing and the date is not the date of the first dose the time assigned is 12:00;
- if the date is the same as the date of the first dose and the only hour is missing the hour assigned is 12 or the hour of the first dose, whichever is later, and if the date is the same as the date of the first dose and only the minute is missing the minute assigned is 30 or the minute of the first dose, whichever is later. Otherwise, the hour assigned is 12 if the hour is missing and the date is not the same as the date of the first dose, and the minute assigned is 30 if the date is not the same as the date of first dose.

#### 7. Study Subjects and Demographics

#### 7.1. Disposition of Subjects and Withdrawals

All subjects who provide informed consent will be accounted for in this study.

The total number of subjects for each of the following categories will be presented overall for the enrolled population:

- Screening Population
- Safety Analysis Set (SAFT)
- Intent-to-treat Population (ITT)
- Modified Intent-to-treat Population (mITT)
- Per Protocol Population (PP)

The total number of screening failures and the reasons for screen failure will be presented overall.

#### 7.2. Protocol Deviations

Protocol deviations will be identified and classified at the data review meeting before defining the analysis populations for the final analysis.

the state of the second se	

All protocol deviations will be listed.

#### 7.3. Demographics and Other Baseline Characteristics

Descriptive summaries of the demographics (age, sex, height, body weight, ethnicity, race, Fitzpatrick skin type) will be completed for each of the following populations: mITT and SAFT.

For the continuous variables, the number of non-missing values and the mean, SD, minimum, median, and maximum will be tabulated.

Descriptive summaries of the medical/surgical history and prior medications will be completed for the Safety population.

Medical/surgical history will be coded with MedDRA dictionary. Incidences of findings in medical history will be summarized by SOC and PT, unless otherwise specified.

The frequency and percentage of prior medications will be summarized using the latest version available at time of the database lock of the World Health Organization Drug Dictionary (WHO-DD) by Anatomical Therapeutic Chemical (ATC) level 2 within level 1.

#### 7.4. Exposure and Compliance

Data will be tabulated for Safety population (SAFT).

Number of treatment sessions will be tabulated in a frequency table for both treatment groups.

Volume to obtain an OCR (initial treatment and touch-up) and volume injected at retreatment will be tabulated in a summary table by treatment group.

Injection technique will be tabulated in a frequency table by treatment group and treatment occasion.

All exposure data will be listed.

Page 31 of 53

#### 8. Effectiveness Analysis

The primary and secondary effectiveness analyses will be based on the mITT population. The analyses will be repeated for the PP population.

For categorical variables, the 2 groups will be compared using independent-testing based on a 2-group, 2-sided, Fisher's exact test. For continuous variables, ANCOVA or applicable non-parametric method will be used.

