7.2. Clinical Investigation Enrollment

This study will enroll at least 200 subjects and a maximum of 202 subjects. Subjects must have lip fullness of grade 1 to 3 on the TLFS (ranging from 1 to 5) and desire at least 1 point of correction.

Eligible subjects will be randomly assigned in a 3:1 ratio to either the RHA[®] 3 or group.

The TI will not be blinded, while the BLE and subjects will be blinded to treatment allocation.

All evaluations performed by the BLE will be performed completely separately from the TI;

Furthermore, to ensure that they remain masked and unbiased when making their assessments throughout the study, the BLE, TI, and the subject will not be allowed to refer to each other's effectiveness assessments.

Page 48 of 132

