11.3. Subjects and Demographics

11.3.2. Clinical Investigation Plan Deviations

A CIP deviation is any noncompliance with the clinical investigation CIP or International Council for Harmonization of Technical Requirements for Pharmaceuticals for Human Use (ICH) GCP requirements. The noncompliance may be either on the part of the subject, the TI, or study site staff. Corrective actions are to be developed by the site and implemented promptly.

It is the responsibility of the site TI to report any CIP deviations after identification. All deviations must be addressed in study source documents and reported to the sponsor. Clinical investigation plan deviations must be sent to the reviewing IRBs as per local regulations. The site TI is responsible for knowing and adhering to the reviewing IRB requirements. Further details about the handling of CIP deviations will be included in the CIP deviation guidance plan.

Confidential
Clinical Investigation Plan
will be collected
11.4. Effectiveness Analyses Effectiveness analyses will be performed primarily on mITT analysis set.
The primary analysis will be performed as follows: to demonstrate non-inferiority of RHA [®] 3 compared to at 12 weeks after the last treatment; the difference in the change will then be tested between groups (RHA [®] 3 minus

Page 91 of 132

Confider	tial
Clinical Investigation Plan	
Secondary Effectiveness Analysis:	
Secondary analyses will be of descriptive nature	

For the parameters hereafter:

- TLFS: BLE
- Responder rate based on TLFS
- GAIS: BLE,
- FACE-Q scores for each module: Subject (after data standardization, as detailed in SAP)
- Subject satisfaction score: Subject (quantitative scores and categories as described in SAP)

		وجداد والمرا	

For each product, summary statistics (mean, minimum, maximum, SD, and 95% CI of the mean) for the above-mentioned parameters will be provided/presented for each study visit.

For endpoints with qualitative results, frequencies and percentages will be calculated and presented for each study visit.

	Confidential	
Clinical Investigation Plan		
	-	

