#### 3.3. Study Population

A potential subject will be included in the study if they meet the inclusion criteria described in the protocol. Subjects shall be 22 years of age or older, seeking lip augmentation

Full list of inclusion/exclusion criteria is described in the protocol.

A total of 200 subjects will be enrolled in the study,

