#### 3.4. Treatment Allocation, Randomization and Blinding

The randomization schedule will be computer generated using a permuted block algorithm and randomly allocate the investigational product in a 3:1 ratio. Subject will be randomized to one of the following groups:

- RHA® 3 study device
- control device.

Randomization numbers with specific treatment assignments will be assigned sequentially in a 3digit subject number, as subjects are entered into the study.

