#### 8.3.4. Subject Satisfaction Score

Subject Satisfaction will be assessed by subjects using the following static 5-grade scale.

Satisfaction grade frequencies and percentages will be calculated and presented for each study visit.

For subject satisfaction, proportions of "satisfied" and "very satisfied" (subject satisfaction responder rate) will be presented, along with the 95% CI of the proportion at each applicable study visit.

Grade description:

Page 35 of 53

Statistical Analysis Plan Protocol Number		

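### SAP 8 sets Fisher's exact test for all categorical effectiveness variables; if it is applied to the five-grade GAIS and Subject Satisfaction scales, it ignores grade order and usually costs some power

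*SAP*

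**What the plan says.** SAP 8 covers both the primary and the secondary effectiveness analyses and gives two general rules for comparing the arms. For categorical data: "For categorical variables, the 2 groups will be compared using independent-testing based on a 2-group, 2-sided, Fisher's exact test". For continuous data: "For continuous variables, ANCOVA or applicable non-parametric method will be used". A non-parametric option is therefore stated for continuous variables only.

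The endpoint sections are narrower:

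- **TLFS responder rate (SAP 8.3.2).** This is binary, and Fisher's exact test is named for each applicable visit.
- **GAIS (SAP text following 8.3.2).** "GAIS grade frequencies and percentages will be calculated and presented for each study visit". The five grades run from much improved to much worse. No between-arm test is visible.
- **Subject Satisfaction (SAP 8.3.4).** "Satisfaction grade frequencies and percentages will be calculated and presented for each study visit". The proportion in the two satisfied grades is also reported with a 95% CI. No between-arm test is visible.

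Protocol 11.4 says "Secondary analyses will be of descriptive nature" and foresees Subject Satisfaction both as a quantitative score and in categories. On size, SAP 3.3 says "A total of 200 subjects will be enrolled in the study", Protocol 7.2 says "This study will enroll at least 200 subjects and a maximum of 202 subjects", and SAP 3.4 will "randomly allocate the investigational product in a 3:1 ratio".

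**The concern.** Fisher's test suits a binary outcome. On a 2x5 table its p-value stays the same however the five columns are reordered, so it cannot use the fact that much improved is better than improved, which is better than no change. It also gives no single measure of the direction or size of a difference.

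Both scales support objectives that run to 52 weeks, and the control arm has only about 50 subjects. If the general rule in SAP 8 is what the programmer follows for these scales, a consistent shift towards better or worse grades is less likely to be detected than it need be. What is at stake is how well two secondary endpoints are read, not the trial's success criterion.

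**Working it through.** **1. Arm sizes.** 200 x 3/4 = 150 RHA 3 and 200/4 = 50 control. With 202 subjects the figures are 151.5 and 50.5. These are randomised counts; the mITT count at a given visit may be lower.

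**2. No planned figure to reproduce.** No power is stated for GAIS or Subject Satisfaction in the visible text. The figures below compare methods under assumptions.

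**3. A single table.** Take illustrative counts in grades 1 to 5 of 75/50/20/4/1 (RHA 3, n=150) and 15/20/11/3/1 (control, n=50).

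- Exact Fisher test on the 2x5 table: p = 0.062. With the columns reordered as grades 3, 1, 5, 2, 4, it is still 0.062.
- Tie-corrected Wilcoxon-Mann-Whitney: p = 0.007.
- Fisher on the top two grades, 125/150 (83.3%) against 35/50 (70.0%): p = 0.064.
- Mann-Whitney probability = (pairs in which the RHA 3 subject is better + half the ties) / (150 x 50).
  - Better: 75x35 + 50x15 + 20x4 + 4x1 = 3459.
  - Ties: 75x15 + 50x20 + 20x11 + 4x3 + 1x1 = 2358.
  - Result: (3459 + 1179)/7500 = 0.618.

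**4. Power under a one-directional shift.** Assumptions: 150 vs 50, two-sided 5%, and three control distributions for grades 1 to 5: A 35/40/20/4/1%, B 50/35/12/2/1%, C 20/40/30/7/3%. If c is the control probability of being in grade k or better, the RHA 3 probability is c' = OR x o / (1 + OR x o), with o = c/(1 - c). Example (A, grade 1, OR 2): o = 0.35/0.65 = 0.538 and c' = 1.077/2.077 = 0.519. There were 3,000 simulated trials per setting (standard error at most 0.9 points).

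| OR | Control | Fisher 2x5 | Wilcoxon | Gain (points) |
|---|---|---|---|---|
| 2.0 | A | 50.4% | 61.9% | 11.5 |
| 2.0 | B | 48.8% | 57.7% | 8.9 |
| 2.0 | C | 49.1% | 63.2% | 14.1 |
| 2.5 | A | 75.9% | 84.7% | 8.8 |
| 2.5 | B | 72.4% | 81.2% | 8.8 |
| 2.5 | C | 75.7% | 86.1% | 10.4 |
| 3.0 | A | 88.9% | 93.5% | 4.6 |
| 3.0 | B | 86.4% | 91.8% | 5.4 |
| 3.0 | C | 89.4% | 95.2% | 5.8 |

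With no difference between arms, both tests reject in 5.0 to 5.5% of trials, so the gain is not bought with false positives. Three other assumed control distributions (35/45/17/2/1, 20/40/35/4/1 and 50/38/8/3/1%) gave 48-51% for Fisher and 57-62% for Wilcoxon at OR 2. A shorter run at OR 2 (300 trials per setting) gave 47-52% and 49-64%, so in some settings the gain may be small.

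**5. Power under a mixed change.** The ranking reverses when best and poor grades both become more frequent. With RHA 3 at 45/30/13/8/4% and control at 30/50/18/1/1%, power is about 77% for 2x5 Fisher and about 10% for Wilcoxon. With 45/30/20/4/1% against 35/45/17/2/1%, it is about 30% and 5 to 7%.

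**The case against.** The strongest reply is that the plan may never apply Fisher's test to five grades. A reader might infer from SAP 8 that it does. The visible text does not establish this: the only endpoint section that names the test is the binary TLFS responder rate, where no order is lost. The text after the GAIS and Satisfaction grade descriptions and the list of planned tables is redacted, and an endpoint-specific method could stand there. Subject Satisfaction may also be analysed as a score, which would bring in the ANCOVA or non-parametric rule; the SAP already summarises the five-grade TLFS with means and SDs. All of this stands, and it is why the point is conditional. It does not remove the point. The legible rule is not limited to binary variables, the score wording covers Satisfaction but not GAIS, and a programmer following SAP 8 literally would run the 2x5 test.

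A second reply is that the protocol calls these analyses descriptive and gives them no visible power target. That stands and lowers the severity. The SAP nevertheless states between-arm tests, and if p-values are produced they should suit the scale.

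A third reply is that the proportional-odds shift is a favourable setting for a rank test. That also stands. The claim that Wilcoxon is better whatever the alternative would be wrong, as step 5 of the check shows.

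**Conclusion.** The point holds in conditional form. SAP 8 sets an order-blind test as the general rule for categorical variables, with no visible exception for ordered scales. If it is applied to the five-grade GAIS or Satisfaction distributions, the typical cost is about 5 to 14 percentage points of power. This assumes 150 vs 50 subjects, a two-sided 5% level, a proportional-odds shift with odds ratios of 2 to 3, and the assumed control distributions. None of the distributions or odds ratios comes from the documents.

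A reader might also infer that the trial's main conclusion is at risk, or that an unfavourable shift on these scales could slip through a non-inferiority claim. The documents do not support this. The visible success rule in SAP 8.1 is the lower CI bound for the TLFS difference against -0.5; GAIS and Satisfaction do not enter it and have no visible margin. The frequency tables by arm would in any case show the direction of a shift. This is a cheap improvement of low severity.

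**What to change.** In SAP 8, limit Fisher's exact test to binary variables, such as the TLFS responder and the satisfaction responder if the latter is compared between arms. Add that, wherever the five-grade GAIS or Subject Satisfaction distributions are compared between arms, a tie-corrected Wilcoxon-Mann-Whitney test is used. For each such comparison, report the Mann-Whitney probability (the chance that a RHA 3 subject has a better grade than a control subject, ties counted as half) with its 95% CI. If no formal comparison of the five grades is intended, one sentence saying so would settle the point.

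Keep the planned frequency tables and responder proportions. They cover the one small downside, which is that a rank test is less sensitive than the 2x5 Fisher test to mixed changes with more best and more poor grades together.

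The cost is one or two sentences in SAP 8 and 8.3 and a standard SAS procedure. No new data, subjects or visits are needed.
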